### 3.2 Inclusion criteria

Patients eligible for inclusion in this early treatment protocol have to meet **all** of the following criteria:

1. Histologically or cytologically confirmed diagnosis of lung adenocarcinoma that demonstrates *ALK* rearrangement as detected by the approved FISH test (Abbott Molecular Inc), using Vysis breakapart probes (defined as 15% or more positive tumor cells); or the Ventana IHC test. Evidence of rearrangement by gene sequencing tests such as FoundationOne or Caris will also be seen as evidence of *ALK* abnormality and meeting eligibility requirement.
2. Patients with no prior *ALK*-inhibitor therapy will be placed in cohort A, those treated with one prior line of *ALK*-inhibitor (at any time) will enter cohort B.
3. Patients will not have any other curative therapeutic option, such as radiation or surgery.
4. WHO performance status 0-2.
5. Age  $\geq$ 18 years.
6. Patients must have recovered from all toxicities related to any prior anticancer therapies to  $\leq$  Grade 2 (CTCAE v 4.03), provided that any concomitant medication is given prior to initiation of

treatment with ceritinib. Exception to this criterion: patients with any grade of alopecia are allowed to enter the treatment.

7. Adequate organ function: the following laboratory criteria have been met:
  - Absolute neutrophil count (ANC)  $\geq 1.5 \times 10^9/L$
  - Hemoglobin (Hgb)  $\geq 8$  g/dL
  - Platelets  $\geq 75 \times 10^9/L$
  - Serum creatinine  $< 1.5$  mg/dL and /or calculated creatinine clearance (using Cockcroft-Gault formula)  $\geq 30$  mL/min
  - Total bilirubin  $\leq 1.5$  x upper limit of normal (ULN), except for patients with Gilbert's syndrome who may be included if total bilirubin  $\leq 3.0$  x ULN or direct bilirubin  $\leq 1.5$  x ULN
  - Aspartate transaminase (AST)  $< 2.0$  x ULN, except for patients with liver metastasis, who are only included if AST  $< 3$  x ULN; alanine transaminase (ALT)  $< 2.0$  x ULN, except for patients with liver metastasis, who are only included if ALT  $< 3$  x ULN
  - Alkaline phosphatase (ALP)  $\leq 5.0$  x ULN
  - Fasting plasma glucose  $\leq 175$  mg/dL ( $\leq 9.8$  mmol/L)
  - Serum amylase  $\leq 2$  x ULN
  - Serum lipase  $\leq$  ULN
8. Patient must have the following laboratory values or have the following laboratory values corrected with supplements to be above the lower limit of normal before the first dose of ceritinib:
  - Potassium
  - Magnesium
  - Phosphorus
  - Total calcium (corrected for serum albumin)
9. Written informed consent for the protocol must be obtained prior to any screening procedures.
10. Willingness and ability to comply with scheduled visits, treatment plans, laboratory tests and other procedures.

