**STUDY SUMMARY**

Title	Phase II trial of Ceritinib in combination with Stereotactic Ablative Radiation in ALK -rearranged metastatic lung adenocarcinoma
Short Title	Ceritinib and SABR in ALK + lung adenocarcinoma
Protocol Number	XXX
Phase	II
Methodology	Open label, Dual arm
Study Duration	Three years
Study Center(s)	single center
Objectives	Prolongation of progression free survival in lung adenocarcinoma with targeted therapy and radiation
Number of Subjects	33
Diagnosis and Main Inclusion Criteria	Metastatic/locally advanced lung adenocarcinoma harboring a ALK rearrangement
Study Product(s), Dose, Route, Regimen	Ceritinib (LDK378) 450 mg PO daily
Duration of administration	Until progression/intolerance of therapy. Projected 14 months for patients who progressed on crizotinib therapy and 20 months for those who have not been treated previously with an ALK inhibitor.
Reference therapy	Published progression free survival with ceritinib (LDK378) alone
Statistical Methodology	Sample size calculated on the basis of prolongation of progression free survival of patients treated on this protocol compared to published survival data. Kaplan Meier Methods will be used to estimate progression-free survival and overall survival

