### **1.5 Rationale for the protocol design**

The purpose of the trial is to determine if the addition of SABR to ceritinib can prolong the clinical benefit of targeted therapy. This will be an open-label, non-randomized, two arm trial in *ALK* + lung adenocarcinoma. The protocol will also report the safety of treating with SABR and ceritinib, though both are widely used in clinical practice.

Crizotinib is widely used for *ALK* + lung adenocarcinoma. Ceritinib is FDA approved as subsequent therapy for *ALK* + lung adenocarcinoma. As both are excellent options for treatment of *ALK*+ lung cancer, the trial will consist of two cohorts. The first will be for patients who have never been treated with an *ALK* inhibitor, the other will be for patients who have progressed on one *ALK* inhibitor.

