## 2.0 Study Objectives

The hypothesis is that delivering SABR to patients with persisting tumors 10 weeks after ceritinib will result in superior overall tumor control, prolong PFS for patients and lengthen the duration of ceritinib activity in patients with *ALK*+ lung adenocarcinoma.

Published experience suggests that median PFS for patients who have previously been treated with crizotinib is less with ceritinib than those who have never been treated with crizotinib (7 months vs 10 months) (Shaw et al, NEJM 2014). As a result patients enrolled on this study will be divided into cohorts on the basis of prior exposure to crizotinib.

The primary endpoint of this study will be Progression-Free Survival (PFS); defined as time from initiation of ceritinib to evidence of disease progression by RECIST 1.1, unacceptable toxicity, withdrawal of consent, or discontinuation of the trial for any other reason.

There may be progression in a specific localized region that is amenable to stereotactic radiation. If all existing lesions that enlarge and any new lesions that develop can still be effectively treated with stereotactic radiation, patients will be evaluated for repeat SABR therapy and ceritinib resumed. This will be at the recommendation of the treating physician according to standard practice. This will be defined as Time to 2nd SABR therapy and will be one of the secondary endpoints.

Similarly, if 3rd round of SABR can be safely provided with subsequent resumption of ceritinib, it will be defined as the Time to 3rd SABR therapy.

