### 3.3 Exclusion criteria

Patients eligible must not meet **any** of the following criteria:

1. Patients with known hypersensitivity to any of the excipients of ceritinib (microcrystalline cellulose, mannitol, crospovidone, colloidal silicon dioxide and magnesium stearate).
2. History of carcinomatous meningitis.
3. Prior therapy with ceritinib.
4. Presence or history of a malignant disease other than lung adenocarcinoma that has been diagnosed and/or required therapy within the past year and is undergoing active anticancer treatment. Exceptions to this exclusion include the following: completely resected basal cell and squamous cell skin cancers, and completely resected carcinoma in situ of any type.
5. Patient has history of interstitial lung disease or interstitial pneumonitis, including clinically significant radiation pneumonitis (i.e., affecting activities of daily living or requiring therapeutic intervention).
6. Patient who has received thoracic radiotherapy to lung fields  $\leq 4$  weeks prior to starting the study treatment or patients who have not recovered from radiotherapy-related toxicities. For all other anatomic sites (including radiotherapy to thoracic vertebrae and ribs) radiotherapy  $\leq 2$  weeks prior

- to starting the study treatment or has not recovered from radiotherapy-related toxicities. Palliative radiotherapy for bone lesions  $\leq 2$  weeks prior to starting study treatment is allowed.
7. Patient has clinically significant, uncontrolled heart disease and/or recent cardiac event (within 6 months), such as:
    - unstable angina within 6 months prior to screening;
    - myocardial infarction within 6 months prior to screening;
    - history of documented congestive heart failure (New York Heart Association functional classification III-IV);
    - uncontrolled hypertension defined by a Systolic Blood Pressure (SBP)  $\geq 160$  mm Hg and/or Diastolic Blood Pressure (DBP)  $\geq 100$  mm Hg, with or without antihypertensive medication
      - initiation or adjustment of antihypertensive medication(s) is allowed prior to screening;
    - ventricular arrhythmias; supraventricular and nodal arrhythmias not controlled with medication;
    - other cardiac arrhythmia not controlled with medication;
    - Corrected QT (QTcF)  $>470$  ms using Fridericia's correction on the screening ECG

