## 9.0 STATISTICAL CONSIDERATIONS

### 9.1 Study Design/Study Endpoints

This is an, open-label, two-cohort protocol designed to evaluate the activity of targeted therapy and SABR in *ALK* positive lung adenocarcinoma.

Cohort A will evaluate the combination in *ALK*-inhibitor naïve patients.

Cohort B will evaluate the combination in patients who have received treatment with one prior *ALK* inhibitor.

Ceritinib will be administered to the patient until disease progression by RECIST 1.1, unacceptable toxicity, withdrawal of consent, or discontinuation of the trial for any other reason including death.

The primary focus of this protocol is identifying response in *ALK*+ lung cancer patients. Patients with IHC positive or FISH probe positive tumors will be treated. Evidence of *ALK* gene rearrangement will also be considered eligible for the trial.

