**Study Design:**

**Purpose:** of this prospective, single-center, two cohort, non-randomized trial is to evaluate the impact of the combination of ceritinib and stereotactic radiation delivered to patients with *ALK*-rearranged adenocarcinoma. The enhanced efficacy of this combination is to be evaluated specifically with regards to prolongation of clinical benefit of ceritinib. We will also evaluate the safety of this combination of targeted therapy and radiation.

For *ALK*-rearranged patients started on ceritinib and treated with SABR to persisting lesions:  
 -PFS compared to published historical results with ceritinib alone PFS=7 month for prior crizotinib treated and 10 month for no previous crizotinib therapy (Shaw et al, NEJM 2014).  
 PFS will be defined as Time to Subsequent Systemic Therapy.

As secondary objectives, we will also report overall survival and time to 2nd and 3rd SABR for each cohort.

	Objective	Endpoint
Primary:	Cohort A: Superiority of ceritinib + SABR median PFS compared to historical control of 10 months (expected to be 20 months)  Cohort B: Superiority of ceritinib + SABR median PFS compared to historical control of 7 months	Cohort A Median PFS defined as time from initiation of ceritinib until disease progression by RECIST 1.1, unacceptable toxicity, withdrawal of consent, or discontinuation of the trial for any other reason including death.  Cohort B: Median PFS defined as time from initiation of ceritinib until disease progression by RECIST 1.1, unacceptable toxicity, withdrawal of consent, or discontinuation of the trial for any other reason including death.
Secondary:	Report Overall survival  Report Time to 2 nd SABR  Report Time to 3 rd SABR  Report proportion of patients CR/PR/stable disease at 6 and 12 months	Overall survival  Time from start of systemic therapy to first day of second course of SABR  Time from start of therapy to first day of third course of SABR  Number of patients with CR/PR/stable disease for 6 and 12 months after initiation
Safety:	Demonstrate safety of ceritinib followed by SABR	Describe toxicity and adverse events (CTCAE v.4) compared to historical controls.

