## 9.2 Sample Size and Accrual

The results of a Phase I trial of ceritinib in *ALK*-rearranged metastatic adenocarcinoma were reported recently (Shaw et al., 2014). Ceritinib demonstrated activity in patients with an overall response rate of 57% at doses of 400 mg or greater. The PFS reported was 7 months for those with prior crizotinib treatment and 10 months for those who had not received any crizotinib. Toxicities and adverse events were also reported. This study offers contemporary, relevant historical control data for comparison purposes.

The sample size calculation is based on the primary endpoint, progression-free survival, and the assumption that patients are randomized until the end of accrual. The sample size is calculated separately for each cohort.

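### Cohort B is defined in several conflicting ways, and its 7-month PFS benchmark is documented only for crizotinib-pretreated patients, although entry is open after other ALK inhibitors

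*Combined protocol and SAP*

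**What the plan says.** The operative entry rule is inclusion criterion 2 in Section 3.2: "those treated with one prior line of *ALK*-inhibitor (at any time) will enter cohort B". It names no agent and does not mention progression. Section 9.1 is equally broad: "Cohort B will evaluate the combination in patients who have received treatment with one prior *ALK* inhibitor". Among prior ALK inhibitors, the exclusion criteria in Section 3.3 bar only one: "Prior therapy with ceritinib".

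Three other places describe a narrower group, each differently:

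- Section 1.5 asks for progression but names no drug: "the other will be for patients who have progressed on one *ALK* inhibitor".
- The Study Summary asks for progression on one named drug: "Projected 14 months for patients who progressed on crizotinib therapy".
- Section 2.0 uses exposure to that drug, without progression: "patients enrolled on this study will be divided into cohorts on the basis of prior exposure to crizotinib".

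The benchmark is always worded by crizotinib. Section 9.2 says: "The PFS reported was 7 months for those with prior crizotinib treatment and 10 months for those who had not received any crizotinib". The Study Design text in Section 9.1 repeats it: "PFS=7 month for prior crizotinib treated and 10 month for no previous crizotinib therapy". Section 9.2 then sizes Cohort B at 15 patients for 80% power, 7 against 14 months, at a two-sided level of 0.1. Section 9.3 plans Kaplan-Meier estimation of PFS. It names no test against 7 months and no analysis by prior agent or by progression on it.

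**The concern.** Comparison with 7 months is the whole primary objective of Cohort B, and there is no concurrent control. The comparison is informative only if 7 months is a fair figure for ceritinib alone in the patients enrolled.

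For a patient whose one prior ALK inhibitor was a drug other than crizotinib, the documents give no PFS on ceritinib. The sections also disagree about where that patient belongs. Criterion 2 sends the patient to Cohort B and a 7-month null. The split in Section 2.0 treats the same patient as not exposed to crizotinib, and the figure given for that group is 10 months. This is a conflict between rules on the primary comparison, and it matters in a cohort of 15, where three patients are 20%.

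**Working it through.** **1. The definitions side by side**

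| Place | Prior drug | Progression required? |
|---|---|---|
| Section 3.2 (criterion 2) with Section 3.3 | any one ALK inhibitor except ceritinib | not stated |
| Section 9.1, cohort description | one ALK inhibitor | not stated |
| Section 1.5 | one ALK inhibitor | yes |
| Study Summary (14-month projection) | crizotinib | yes |
| Section 2.0 | crizotinib | not stated |
| 7-month figure (2.0, 9.1, 9.2) | crizotinib | not stated |

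Only Section 2.0 matches the benchmark. Section 1.1.2 does give 6.9 months for patients previously treated with an ALK inhibitor, but that is duration of response, not PFS.

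**2. The plan's own sample size**

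Inputs from Section 9.2: n = 15, medians 7 and 14 months, two-sided level 0.1 (z = 1.645), accrual A = 36 months, follow-up F = 12 months. Assume exponential PFS and uniform accrual, with hazard l = ln 2 / median.

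- P(event) = 1 − [exp(−lF) − exp(−l(A+F))] / (lA).
- Null: l = 0.0990, P0 = 1 − (0.3048 − 0.0086)/3.565 = 0.917, so 13.75 expected events.
- Alternative: l = 0.0495, P1 = 1 − (0.5520 − 0.0929)/1.782 = 0.742, so 11.14 expected events.
- Power of a log-hazard test = Φ[(ln 2 − 1.645/√13.75) × √11.14] = Φ[(0.693 − 0.444) × 3.337] = Φ(0.83) = 79.8%.

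The smallest n for 80% by this formula is 16. The stated 15 is reproduced within the accuracy of the approximation and is not disputed.

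**3. Sensitivity to the control median**

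Take n = 15 tested against 7 months, with no SABR effect. The upper-tail error is nominally 5%. Over three approximations (log-hazard, cube-root, one-sample log-rank) it becomes 1-2% if the true ceritinib-alone median is 6 months and 11-13% if it is 8 months.

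**4. Mixed cohorts**

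Simulation with 200,000 trials per scenario, exponential PFS and the accrual and follow-up above. The test is the one-sample log-rank, success if (E − O)/√E > 1.645, where O is observed events and E is total follow-up time × ln 2 / 7. The shares and the non-7-month medians are assumptions. The 10-month value borrows the documents' crizotinib-naive figure.

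| Scenario | Chance of declaring success |
|---|---|
| No SABR effect, all at 7 months | 3.5% |
| No effect, 10% at 10 months | 5.0% |
| No effect, 20% at 10 months | about 7% |
| No effect, 33% at 10 months | 9.7% |
| No effect, 50% at 10 months | 14.4% |
| SABR doubles PFS, all 7 to 14 months | 76% |
| Doubling, one third from 5 to 10 months | 64% |
| Doubling, one third from 3.5 to 7 months | 50% |

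**5. Cost of restricting the tested set**

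With the same test and 7 doubled to 14 months, power is 76% at n = 15, about 67% at n = 12 and about 60% at n = 10.

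**The case against.** The strongest reply is that the benchmark is worded by exposure to crizotinib, not by progression on it. A patient who stopped crizotinib for intolerance therefore fits the group to which 7 months is attached. This stands. A reader might infer that such patients lie outside the benchmark and resemble the naive group, or that Cohort B must require progression on crizotinib to match it. The documents support neither. Section 1.3.1 mentions phase I patients who failed crizotinib but does not link them to the 7 months. Nor is it right that progression is simply missing from the plan: Section 1.5 and the Study Summary state it, while the eligibility and statistical sections do not.

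A second reply is that Section 1.1.2 divides the same phase I study into 163 patients previously treated with an ALK inhibitor and 83 naive, the same split as criterion 2, so that crizotinib may be loose shorthand. That is possible. But every PFS figure is worded by crizotinib, and the documents nowhere say that the two groups coincide.

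A third reply is that the error rates rest on assumed shares and medians and on a test the plan does not name. That is correct. The 3.5% starting point is below the nominal 5%, and if 20% of patients sat midway at 8.5 months, false success would be only about 5%. Uncertain attribution is also a limit of any single-arm comparison with a published median, however criterion 2 is worded.

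**Conclusion.** The point holds as a conflict of definitions affecting Cohort B's primary comparison, and it should be fixed. Firmly established are the differing descriptions of Cohort B, the documentation of 7 months for crizotinib-pretreated patients only, and the open entry after other ALK inhibitors except ceritinib.

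The size is conditional. False success of 5-14% (from 3.5%) requires 10-50% of the cohort to have a 10-month benchmark. Power of 50-64% (from 76%) requires one third to have a 3.5-5 month benchmark. Both assume exponential PFS and a one-sample log-rank test. A reader might infer that Cohort B's result will be biased, or biased in favour of SABR. The documents do not show this: they give no ceritinib PFS after another ALK inhibitor or after stopping one without progression, and do not say how many such patients would enter. The sample size itself stands.

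**What to change.** 1. Reconcile the Study Summary and Sections 1.5, 2.0, 3.2 and 9.1 to one Cohort B definition, stating the prior drug and whether progression on it is required.
2. State in Section 9.3 that the comparison with 7 months is made in crizotinib-pretreated patients. Prior antineoplastic medication is already collected under Sections 5.1.3 and 5.2.1.2, so this can be applied to patients already enrolled.
3. If patients pretreated with another ALK inhibitor remain eligible, describe their PFS separately, with no test against 7 months.
4. Add a sensitivity analysis by progression status on the prior inhibitor, and repeat the comparison over a stated range of control medians, for example 6 to 8 months. The documents do not list the reason for stopping the prior inhibitor as a data item, so it may need to be added.

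The text changes are small. The real cost is a smaller tested set: losing three of 15 patients takes power from about 76% to 67%, and losing five takes it to about 60%. That loss is similar in size to the power loss in the mixed-cohort scenarios, so the plan should state it, or Cohort B should accrue until the tested set reaches 15, at the price of slower accrual.

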### 3.3 Exclusion criteria

Patients eligible must not meet **any** of the following criteria:

1. Patients with known hypersensitivity to any of the excipients of ceritinib (microcrystalline cellulose, mannitol, crospovidone, colloidal silicon dioxide and magnesium stearate).
2. History of carcinomatous meningitis.
3. Prior therapy with ceritinib.
4. Presence or history of a malignant disease other than lung adenocarcinoma that has been diagnosed and/or required therapy within the past year and is undergoing active anticancer treatment. Exceptions to this exclusion include the following: completely resected basal cell and squamous cell skin cancers, and completely resected carcinoma in situ of any type.
5. Patient has history of interstitial lung disease or interstitial pneumonitis, including clinically significant radiation pneumonitis (i.e., affecting activities of daily living or requiring therapeutic intervention).
6. Patient who has received thoracic radiotherapy to lung fields  $\leq 4$  weeks prior to starting the study treatment or patients who have not recovered from radiotherapy-related toxicities. For all other anatomic sites (including radiotherapy to thoracic vertebrae and ribs) radiotherapy  $\leq 2$  weeks prior

- to starting the study treatment or has not recovered from radiotherapy-related toxicities. Palliative radiotherapy for bone lesions  $\leq 2$  weeks prior to starting study treatment is allowed.
7. Patient has clinically significant, uncontrolled heart disease and/or recent cardiac event (within 6 months), such as:
    - unstable angina within 6 months prior to screening;
    - myocardial infarction within 6 months prior to screening;
    - history of documented congestive heart failure (New York Heart Association functional classification III-IV);
    - uncontrolled hypertension defined by a Systolic Blood Pressure (SBP)  $\geq 160$  mm Hg and/or Diastolic Blood Pressure (DBP)  $\geq 100$  mm Hg, with or without antihypertensive medication
      - initiation or adjustment of antihypertensive medication(s) is allowed prior to screening;
    - ventricular arrhythmias; supraventricular and nodal arrhythmias not controlled with medication;
    - other cardiac arrhythmia not controlled with medication;
    - Corrected QT (QTcF)  $>470$  ms using Fridericia's correction on the screening ECG
  8. Impaired GI function or GI disease that may alter absorption of ceritinib or inability to swallow up to five ceritinib capsules daily. Although, patients unable to swallow capsules will be allowed to participate in this study, by following the specific instructions on making a slurry of the medication.
  9. Patient has impairment of GI function or GI disease that may significantly alter the absorption of ceritinib (e.g., ulcerative diseases, uncontrolled nausea, vomiting, diarrhea, or malabsorption syndrome).
  10. Receiving medications that meet one of the following criteria and that cannot be discontinued at least 1 week prior to the start of treatment with ceritinib and for the duration of participation (see Appendix 1 Tables):
    - Medication with a known high risk of prolonging the QT interval or inducing Torsades de Pointes (please refer to <http://www.azcert.org/medical-pros/drug-lists/drug-lists.cfm>)
    - Strong inhibitors or strong inducers of CYP3A4/5 (please refer to <http://medicine.iupui.edu/flockhart/table.htm> or <http://www.druginteractioninfo.org>)
    - Medications with a low therapeutic index that are primarily metabolized by CYP3A4/5, CYP2C8 and/or CYP2C9 (please refer to <http://medicine.iupui.edu/flockhart/table.htm> or <http://www.druginteractioninfo.org>)
    - Therapeutic doses of warfarin sodium (Coumadin) or any other coumadin-derived anti-coagulant. Anticoagulants not derived from warfarin are allowed (eg, dabigatran, rivaroxaban, apixaban).
    - Unstable or increasing doses of corticosteroids; If patients are on corticosteroids for endocrine deficiencies or tumor-associated symptoms (non-CNS), dose must have been stabilized (or decreasing) for at least 5 days before first dose of study treatment.
    - Enzyme-inducing anticonvulsive agents
    - Herbal supplements
  11. Pregnant or nursing (lactating) women, where pregnancy is defined as the state of a female after conception and until the termination of gestation, confirmed by a positive hCG laboratory test.
  12. Women of child-bearing potential, defined as all women physiologically capable of becoming pregnant, unless they are using highly effective methods of contraception during dosing and agree to continue for 3 months after the last dose of study treatment. Highly effective contraception methods include:

- Total abstinence (when this is in line with the preferred and usual lifestyle of the subject. Periodic abstinence (e.g., calendar, ovulation, symptothermal, post-ovulation methods) and withdrawal are not acceptable methods of contraception.
- Female sterilization (have had surgical bilateral oophorectomy with or without hysterectomy) or tubal ligation at least six weeks before taking study treatment. In case of oophorectomy alone, only when the reproductive status of the woman has been confirmed by follow up hormone level assessment.
- Male sterilization (at least 6 months prior to screening) with the appropriate post-vasectomy documentation of the absence of sperm in the ejaculate. For female subjects on the study the vasectomized male partner should be the sole partner for that subject.
- Combination of any two of the following (a+b or a+c or b+c):
  - a. Use of oral, injected or implanted hormonal methods of contraception or other forms of hormonal contraception that have comparable efficacy (failure rate < 1%), for example hormone vaginal ring or transdermal hormone contraception.
  - b. Placement of an intrauterine device (IUD) or intrauterine system (IUS).
  - c. Barrier methods of contraception: Condom or Occlusive cap (diaphragm or cervical/vault caps) with spermicidal foam/gel/film/cream/vaginal suppository.

In case of use of oral contraception, women should have been stable on the same pill for a minimum of 3 months before taking study treatment.

Women are considered post-menopausal and not of child bearing potential if they have had 12 months of natural (spontaneous) amenorrhea with an appropriate clinical profile (e.g., age appropriate, history of vasomotor symptoms) or have had surgical bilateral oophorectomy (with or without hysterectomy) or tubal ligation at least six weeks prior to screening. In the case of oophorectomy alone, only when the reproductive status of the woman has been confirmed by follow up hormone level assessment is she considered not of child bearing potential.

13. Sexually active males unless they agree to use a condom during intercourse while taking drug and agree to continue for 3 months after the last dose of study treatment. Male patients for 3 months should not father a child in this period. A condom is required to be used also by vasectomized men in order to prevent delivery of the drug via seminal fluid.
14. Patient has a history of pancreatitis or history of increased amylase or lipase that was due to pancreatic disease.
15. Patient has other severe, acute, or chronic medical conditions including uncontrolled diabetes mellitus or psychiatric conditions or laboratory abnormalities that, in the opinion of the investigator, may increase the risk associated with study participation or may interfere with the interpretation of study results.
16. Patient has had major surgery (e.g., intra-thoracic, intra-abdominal or intra-pelvic) within 4 weeks prior to starting study treatment or has not recovered from side effects of such procedure. Video-assisted thoracic surgery (VATS) and mediastinoscopy will not be counted as major surgery and patients can receive study treatment  $\geq 1$  week after these procedures.

